9.1.3 Demographics

The following information will be obtained for each patient: date of birth, sex, race, and ethnicity (as allowed per local regulations). Details informing amount of time spent with main caregiver will also be collected.

9.1.4 Medical History

Relevant, significant medical history will be obtained at Screening (Visit 1) and is defined as any condition or disease that:

- May affect the condition under study.
- Is ongoing on entry into the trial.
- Suspected or confirmed COVID-19 infection (or other significant infectious diseases) within 1 year prior to Screening (Visit 1).
- Information on ASD history, including known etiologies, will be recorded.

9.1.5 Concomitant Medications and Interventions

Details of all current and recent medication/therapy (i.e., taken within the 14 days prior to the initial screening visit) will be recorded. All medications and interventions for ASD related symptoms must remain at stable doses throughout the trial; however, doses may be changed in response to a safety concern. Interventions would include special diets.

Any changes in concomitant medication or interventions during the trial must be recorded on the CRF at trial visits. Patients should stop taking any prohibited therapy prior to the screening visit, as defined in Section 8.3.

Testing for drugs of abuse will be performed at screening (Visit 1).

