6.1 Inclusion Criteria

For inclusion in the trial patients must fulfill ALL of the following criteria:

- 6.1.1 Male or female aged 6 to 17 years (inclusive).
- 6.1.2 Patient weight is at least 12 kg.
- 6.1.3 Patients (if possessing adequate understanding, in the investigator's opinion) and their parent(s)/legal representative are willing and able to give informed consent for participation in the trial.
- 6.1.4 Patient is/and their caregiver are willing and able (in the investigator's opinion) to comply with all trial requirements.
- 6.1.5 Patient has a diagnosis of ASD as per DSM-5 criteria for ASD, confirmed by ADOS-2 criteria (conducted within 2 years at the trial site or at screening by a qualified assessor). Note: During special circumstances (e.g., COVID-19 pandemic) where the ADOS-2 cannot be performed due to site restrictions (e.g., mandatory use of face masks) and an ADOS-2 conducted within 2 years at the trial site by a qualified assessor is not available, eligibility can be confirmed using: 1) an ADOS-2 performed within 2 years by a qualified assessor external to the site; 2) if 1) is not available, eligibility may be confirmed using the ADI-R at screening.
- 6.1.6 CGI-S \geq 4 (moderately ill) at screening and randomization.
- 6.1.7 ABC-I subscale score \geq 15 at screening.
- 6.1.8 IQ \geq 70 at screening, measured within 1 year of screening, using WASI-II.
- 6.1.9 All medications or interventions (including psychosocial interventions, dietary supplements, probiotics, speech therapy, etc.) for ASD related symptoms must have been stable for 4 weeks prior to screening and randomization, and the patient/caregiver should be willing to maintain a stable regimen throughout the trial.
- 6.1.10 Patient must have the ability to swallow the IMP provided as a liquid solution.
- 6.1.11 Patient and/or parent(s)/legal representative is willing to allow the responsible authorities to be notified of participation in the trial, if mandated by local law.
- 6.1.12 Patient and/or parent(s)/legal representative is/are willing to allow the patient's primary care practitioner (if they have one) and consultant (if they have one) to be notified of participation in the trial if the primary care practitioner/consultant is different from the investigator.

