6.2 Exclusion Criteria

The patient may not enter the trial if ANY of the following apply:

- 6.2.1 Current diagnosis of bipolar disorder, psychosis, schizophrenia, schizoaffective disorder or major depression (patients with depression in remission may be included).
- 6.2.2 Has a diagnosis other than ASD that dominates the clinical presentation (e.g., ADHD).
- 6.2.3 Has a progressive neurological condition.
- 6.2.4 Seizures in the past 24 weeks.
- 6.2.5 Changes in anticonvulsive therapy within the last 12 weeks.
- 6.2.6 Currently taking more than 2 AEDs.
- 6.2.7 Taking sirolimus, everolimus, temsirolimus, or tacrolimus.
- 6.2.8 Taking clobazam.
- 6.2.9 Taking omeprazole, lansoprazole, tolbutamide, or warfarin.
- 6.2.10 Taking repaglinide, pioglitazone, rosiglitazone, montelukast, bupropion, or efavirenz.
- 6.2.11 Patient is currently using or has used recreational or medicinal cannabis, cannabinoidbased medications (including Sativex®, or Epidiolex®/Epidyolex®) within the 12 weeks prior to screening and is unwilling to abstain for the duration of the trial.
- 6.2.12 Patient has any known or suspected hypersensitivity to cannabinoids or any of the excipients of the IMP, such as sesame oil.
- 6.2.13 Patient has moderately impaired hepatic function at screening, defined as serum ALT or $AST > 2 \times ULN$ or $TBL > 2 \times ULN'$.
- 6.2.14 This criterion can only be confirmed once the laboratory results are available; patients enrolled into the trial who are later found to meet this criterion must be screen-failed.
- 6.2.15 Patient is male and fertile (i.e., after puberty unless permanently sterile by bilateral orchidectomy) unless willing to ensure that they use male contraception (condom) or remain sexually abstinent during the trial and for 12 weeks thereafter.
- 6.2.16 Patient is female and of childbearing potential (i.e., following menarche and until becoming postmenopausal for ≥ 12 consecutive months unless permanently sterile by hysterectomy, bilateral salpingectomy, or bilateral oophorectomy) unless willing to ensure that they use a highly effective method of birth control (e.g., hormonal contraception, intrauterine device/hormone-releasing system, bilateral tubal occlusion, vasectomized partner, sexual abstinence) during the trial and for 12 weeks thereafter.
- 6.2.17 Female patient who is pregnant (positive pregnancy test), lactating or planning pregnancy during the course of the trial or within 12 weeks thereafter.

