8.3 Prohibited Therapy During Trial Period

The following medications are prohibited for the duration of the trial beginning from the date of the screening visit. However, any patients taking these medications after randomization should not be discontinued from treatment unless there are safety concerns.

Care should be taken with drugs, or their metabolites, that are cytochrome P450 2C19 substrates, such as N-desmethylclobazam and are excluded as indicated below. Care should also be taken with drugs, or their metabolites, that are solely or primarily metabolized by UDP-glucuronosyltransferase 1A9 and 2B7.

- Sirolimus, everolimus, temsirolimus, or tacrolimus.
- Clobazam.
- Omeprazole or lansoprazole.
- Tolbutamide or warfarin.
- Repaglinide, pioglitazone, rosiglitazone, montelukast, bupropion, or efavirenz.
- Any new medications or interventions for ASD related symptoms or changes in dosage, within 4 weeks or during the trial.
- Recreational or medicinal cannabis or cannabinoid-based medications (including Sativex, Epidiolex/Epidyolex) within the 12 weeks prior to or during the trial.
- Any other IMP taken as part of a clinical trial within the 12 weeks prior to or during the trial.

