9.1 Trial Procedures

9.1.1 Informed Consent

The parent(s)/legal representative of minor patients must personally sign and date the IRB/EC approved ICF before any trial-specific procedures are performed or any patient-related data is recorded for the trial. In addition, assent will be taken (if allowed per local regulations) along with parent(s)/legal representative consent, using IRB/EC-approved forms. It is expected that the majority of patients will have sufficient understanding to provide assent; if the investigator assesses the patient as not having sufficient understanding or communication ability to provide assent, this must be clearly recorded in the patient notes. The explicit wish of a minor, who is capable of forming an opinion and assessing the information provided, to refuse participation in or to be withdrawn from the clinical trial at any time must be considered by the investigator. Investigators must record in the patient notes any reason(s) why a minor is unable to sign a form.

The original signed ICF should be retained and a copy provided to the patient and/or parent(s)/legal representative. Patients/parent(s)/legal representative will be given the option of being informed about the summary outcome and results of the trial as part of the ICF. For further details, see Section 15.2.

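### Protocol 9.1.5 has prohibited drugs stopped before the screening visit, where consent is taken, and the named drugs carry no stated look-back

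*Protocol*

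**What the plan says.** Section 9.1.5 of the protocol gives the instruction: "Patients should stop taking any prohibited therapy prior to the screening visit, as defined in Section 8.3". Section 8.3, to which it refers, opens: "The following medications are prohibited for the duration of the trial beginning from the date of the screening visit".

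Section 8.3 then lists two kinds of item.

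- Five bullets name 15 drugs (4 + 1 + 2 + 2 + 6), with no interval attached. The matching exclusions, 6.2.7 to 6.2.10, are in the present tense and cover current use only.
- Three bullets carry their own windows. ASD treatment: "Any new medications or interventions for ASD related symptoms or changes in dosage, within 4 weeks or during the trial". Cannabis and cannabinoids: "including Sativex, Epidiolex/Epidyolex) within the 12 weeks prior to or during the trial". Trial drugs: "Any other IMP taken as part of a clinical trial within the 12 weeks prior to or during the trial".

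The eligibility criteria set windows too. Under 6.1.9, treatments "for ASD related symptoms must have been stable for 4 weeks prior to screening and randomization". Exclusion 6.2.5 reads: "Changes in anticonvulsive therapy within the last 12 weeks".

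On consent, Section 9.1.1 says that the parents or legal representative "must personally sign and date the IRB/EC approved ICF before any trial-specific procedures are performed". Section 15.2 requires written consent before the patient is involved in the trial at all. The Synopsis and Appendix 1 schedule consent at Visit 1, which is the screening visit.

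**The concern.** An instruction to stop a drug before the visit at which consent is given puts a trial-driven change of treatment outside both consent and the oversight that starts with it. The patients are aged 6 to 17, and the listed drugs include clobazam, which Section 3.2 mentions in connection with seizure treatment. A family that followed the sentence for an anticonvulsant or an ASD treatment could stop it for a trial the child then cannot enter, and 9.1.5 does not say so.

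There is a smaller measurement issue. ABC-I of at least 15 at screening and CGI-S of at least 4 at screening and randomization decide who enters, and Visit 2 normally supplies the baseline for every change score. If stopping a drug alters behavior, scores taken soon afterwards may not reflect the patient's usual state.

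**Working it through.** No sample size, power or alpha figure in the plan depends on this point, so there is no plan figure to reproduce. The check is one of sequence and day counts.

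**1. Order of events.** Section 9.1.5 puts the stop before Visit 1. The Synopsis and Appendix 1 put consent at Visit 1, and no earlier consent visit is scheduled. Sections 9.1.1 and 15.2 put consent first. The literal order is therefore stop, then consent, which is the reverse of what the consent sections require. Section 8.3 reinforces this: because its ban starts on the date of the screening visit, a patient still taking a named drug when consent is signed is already in breach that day. Changing 9.1.5 alone would leave that difficulty in place.

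**2. Do the 4-week and 12-week rules still work?** Being off a drug before screening is a necessary condition. It does not replace a longer window that also applies.

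| Recent stop | Criterion that still applies | Result |
|---|---|---|
| Treatment for ASD symptoms (including bupropion if so used) | 6.1.9 and 8.3, 4 weeks | Not eligible |
| Anticonvulsant (including clobazam if so used) | 6.2.5, 12 weeks | Not eligible |
| Another trial drug | 6.2.18 and 8.3, 12 weeks | Not eligible |
| Named drug used for neither ASD symptoms nor seizures | 6.2.7 to 6.2.10, current use only | No look-back; can be eligible |

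Only the last row leaves a gap.

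**3. Length of the gap.** Inputs: 7 to 14 days from screening to randomization (Section 4.1), and baseline as the last measure before the first dose (protocol 13.4, SAP 4.2), normally at Visit 2.

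Stop-to-baseline gap = days off drug before Visit 1 + (7 to 14).

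- Named drug with no look-back, stopped the day before Visit 1: 1 + 7 = 8 to 1 + 14 = 15 days. The screening ABC-I and CGI-S fall 1 day after stopping.
- ASD treatment changed 4 weeks before screening: 28 + 7 = 35 to 28 + 14 = 42 days.
- Another trial drug, 12 weeks before screening: 84 + 7 = 91 to 84 + 14 = 98 days.

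**4. What is recorded.** Section 9.1.5 requires medication taken in the 14 days before screening to be recorded, so a stop 1 day before is visible. A stop 15 or more days before screening lies outside that required record, although 6.1.9 looks back 28 days and 6.2.5 looks back 84. SAP Section 4.5 also accepts a medication stop date with the day or month unknown, which would not support a day count.

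**5. Effect on the comparison.** Assignment is 1:1 and double-blind. Stopping happens before randomization, so any recovery or discontinuation effect is expected equally in both arms. It can add variance to entry and baseline scores; it has no expected direction in the treatment difference.

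**The case against.** The best defense is that the sentence means only that patients must already be off these drugs when they arrive. The exclusions shut out current users and invite no washout, the protocol addresses investigators rather than families, and Sections 7, 9.1.1 and 15.2 all guard consent. Appendix 1 already schedules medication and eligibility reviews at both Visits 1 and 2. Much of this stands, and that may well be the intended meaning. But the sentence is written as an instruction to stop, and nothing in 9.1.5 or 8.3 confines it to patients who had stopped for other reasons.

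It can also be said that the affected group is narrow: a patient aged 6 to 17 on a named drug, for neither ASD symptoms nor seizures, who stopped within days of screening. Current major depression (6.2.1) and other dominant diagnoses (6.2.2) are excluded in any case, and nothing in the documents shows that stopping most of the listed drugs would move ABC-I or CGI-S. That stands. The number could be zero.

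A reader might infer that 9.1.5 contradicts the 4-week and 12-week rules and so lets patients reach baseline days after stopping an ASD treatment or an anticonvulsant. The documents do not support this. Section 9.1.5 defers to 8.3, which carries its own windows, and 6.1.9 and 6.2.5 keep exactly those patients out. Nor should the 8 to 15 days be set against 28 or 84 days as a shortfall: those intervals govern other treatments, and the 28 days is counted to screening, not to baseline.

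**Conclusion.** The point holds as a conflict of wording that bears on patient protection. Read literally, 9.1.5 places a trial-driven stop ahead of consent, contrary to 9.1.1 and 15.2, and it does not warn that the stop may itself make the patient ineligible. This needs no assumption beyond the literal reading and the scheduled place of consent.

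The secondary point is limited to named drugs used for neither ASD symptoms nor seizures. For these the shortest stop-to-baseline gap the text allows is 8 to 15 days, assuming a stop the day before Visit 1 and the 7 to 14 day screening interval. The documents give no basis for estimating how many of the 160 patients this could touch. A reader might go on to infer a biased treatment effect, but blinded 1:1 randomization does not support that; added noise is the most that can be claimed, and its size is not shown.

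**What to change.** Reconcile Sections 9.1.5, 8.3, 9.1.1, 15.2 and 6.2.7 to 6.2.10.

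- Reword the 9.1.5 sentence so that it does not direct any treatment to be stopped for the trial before consent, and align the starting point of the ban in 8.3 with the new wording.
- In the same place, point to 6.1.9 and 6.2.5, so that sites see that a recent stop can make the patient ineligible.
- Have the sponsor's medical team state whether, and how, recent use of the named drugs bears on eligibility. No interval or clinical rule is proposed here.
- Record the stop date of any listed drug, complete where possible, in the medication and eligibility reviews already scheduled at Visits 1 and 2.

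The cost is a wording amendment and one item on existing forms. No visit, assessment or analysis changes. Any effect on recruitment depends on what the medical team decides.

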9.1.6 Physical Examination

Physical examinations will include height (measured once), body weight measurements, and BMI (Visit 1 only).

9.1.7 Vital Signs

Vital sign measurements (body temperature, pulse rate, respiration rate), including blood pressure taken in a sitting position at rest for 5 minutes. Blood pressure must be recorded using the same arm throughout the trial, where possible.

9.1.8 12-Lead Electrocardiogram

A 12-lead ECG will be performed after 5 minutes in a supine position. A physician must review the ECG immediately (annotated, signed and dated) and any abnormal findings considered to indicate significant medical history or AEs must be recorded appropriately on the CRF. Additional ECG measurements can be taken at any time during the trial, if clinically indicated.

9.1.9 Clinical Laboratory Sampling

The investigator should use their judgment and knowledge of the patient to determine when best to collect the blood and urine samples in order to mitigate the risk that invasive procedures may cause the patient to become stressed, thereby affecting the results of other assessments.

Laboratory tests will include hematology, biochemistry, coagulation (Visit 1 only; thereafter only as an unscheduled assessment if ALT or $AST > 3 \times ULN$) and urinalysis (provided urine can be obtained). Blood sample volume requirements and processing procedures will be detailed in a separate laboratory manual.

Urine samples for biochemistry will be analyzed at the trial site (or by the home nurse) by use of a dipstick with any relevant findings being sent for further urinalysis at the central laboratory (urinalysis, microscopy, culture, and sensitivity, as applicable). In cases where urine samples cannot be analyzed at the site (or by the home nurse) due to local regulations, a full set of urine samples should be sent to the central laboratory for analysis. Urine sample volume requirements and processing procedures will be detailed in a separate laboratory manual.

Urine samples for drugs of abuse will be sent to the central laboratory.

The investigator and trial monitor will be provided with a list of the normal ranges used by the testing laboratory for all variables assayed during the trial and a statement of accreditation (or similar) for the laboratory. Clinical laboratory sample parameters are detailed in Table 9.1-1.

Table 9.1-1Biochemistry, Hematology, Urinalysis, and THC					
Biochemistry (Serum) ^a	Hematology (Whole Blood) ^a	Coagulation (plasma) ^{a,b}	Urinalysis (Urine) ^c	Pregnancy Test (Serum) ^a	Drugs of Abuse (Urine) ^a
Alanine aminotransferase (ALT)	Hematocrit	Prothrombin time (PT/INR)	Bilirubin	Serum	Amphetamines
Albumin	Hemoglobin		Blood		Barbiturates
Alkaline phosphatase	Mean cell volume		Glucose		Benzodiazepine
Aspartate aminotransferase (AST)	Mean corpuscular hemoglobin		Ketones		Cannabinoids
Calcium	Platelets		Protein		Cocaine
Creatinine	Red blood cell count		Nitrites		Methadone
Creatinine clearance	White blood cell count with automated differential		рН		Opiates
Creatine kinase (CK)			Specific gravity		MDMA
Gamma-glutamyl transferase			Urobilinogen		Methamphetamines
Glucose			White blood cells		Oxycodone
HDL-cholesterol					Phencyclidine
Potassium					Tricyclic antidepressants
Prolactin					
Sodium					
Total bilirubin					
Total protein					
Triglycerides					
Urea (blood urea nitrogen [BUN])					

HDL = high density lipoprotein; INR = international normalized ratio;

MDMA = 3,4-methylenedioxymethamphetamine: THC = tetrahydrocannabidiol.

^a Analyzed at a central laboratory.

^b Tested at Visit 1 only; thereafter only as an unscheduled assessment only if ALT or $AST > 3 \times ULN$

^c Analyzed at the trial site (or by the home nurse) by use of a dipstick (if allowed per local regulations).

Investigators at trial sites will be notified of safety laboratory test results. All laboratory results will be reviewed, and the reports signed and dated by an investigator. Any results considered to be of clinical significance must be addressed and followed up as clinically appropriate. The results of drugs of abuse screening will be reported back to the trial center for confirmation of eligibility. All laboratory results considered to represent an AE must be documented on the CRF. For reporting and follow-up of potential cases of drug-induced liver injury, see Section 12.7.

Repeat samples will be taken, if required, for clinical follow-up or if the sample is lost or damaged. Any abnormal end of treatment clinical laboratory result of clinical significance must be repeated at regular intervals until it returns to normal, or until an investigator is satisfied that

the abnormality is not related to the IMP and needs no further investigation. Blood sample volume requirements and processing procedures will be detailed in a separate laboratory manual; the maximum amount of blood taken during the course of the trial will not exceed 3 mL/kg of body weight within any 8-week period.

9.1.10 Randomization and Trial Supply Management System

The RTSM system will be used to assign patients to treatment arms, manage IMP supply, and to provide treatment allocation information in the event of patient unblinding. The RTSM system information can be accessed via the eCRF. A member of the trial team must register in the eCRF at clinic visits in order to:

- Obtain a patient number.
- Randomize a patient.
- Obtain dispensing information.

Training will be given to all sites prior to the start of the trial.

9.1.11 Questionnaires and Assessments Completed at Scheduled Visits

Caregiver-completed questionnaires should be completed by an identified main caregiver, nominated at Visit 1. The main caregiver should be able to assess the patient based on daily contact and be able to attend clinic and video call visits. For both caregiver-completed and investigator-completed questionnaires, the same assessors should answer/complete the questionnaires/assessments throughout the trial to maintain consistency. Investigators must be suitably qualified to perform each assessment/administer each questionnaire. Caregiver questionnaires are to be completed electronically at site or at home. Physician interviews/assessments are to be completed at site or over a video call. Visit 2 and Visit 8 assessments should always be completed at site.

If at any point of the trial the main caregiver cannot attend a visit (and this cannot be avoided), an alternate or backup caregiver may be used. This should only be done if all other options for the primary caregiver (i.e., scheduling issues) have been exhausted. The alternative caregiver should not complete the **a**ttended.

